According to the US Surgeon General, there is no known safe amount of alcohol during pregnancy. The Host, Agent, and Environment model has guided our thinking from the start of SA research. This mainstream, utilitarian, analytic tool provides a distinctive, multivariate and multi-disciplinary understanding of prenatal alcohol exposure. Principles of Motivational Interviewing¹¹ and Community-Reinforcement Approach^{12,13} have been shown efficacious in promoting behavior change (reduced alcohol consumption) in several settings.¹⁴⁻¹⁸ Ingersoll et al (2005) reported that a one-session motivational interview-based interview reduced risk for alcohol-exposed pregnancies compared to controls who received a pamphlet on women's health. Others reported greater reduction in alcohol consumption following brief interventions.¹⁸ Potential benefits of this intervention include: women reduce or stop alcohol consumption during pregnancy which results in less or no prenatal alcohol exposure to the developing fetus. Therefore, the public health burden associated with prenatal alcohol exposure is reduced.

STUDY OBJECTIVE

The purpose of the study is to determine the efficacy of a one-session, motivational enhancement therapy intervention to reduce Alcohol Use Disorder Identification Test (AUDIT) scores compared to a comparison group which only receives pamphlets on the risks associated with alcohol consumption during pregnancy.

Primary Objective: To determine whether there is a greater reduction (change) in AUDIT scores from baseline to follow-up in the intervention group relative to the comparison group.

STUDY DESIGN

Setting

The study will be carried out in a single Municipal Area and surrounding rural areas in the Western Cape Province of SA. Afrikaans, English, and Xhosa are the dominate languages in the study area.

Procedures

Pregnant women who sought prenatal care at local clinics will be screened for study eligibility. To be eligible females must be 15-44 years of age, \leq 20 weeks gestation, and at risk for having an alcohol-exposed pregnancy (e.g., drank within the past 30 days). Up to 400 women will be enrolled into the intervention study. Enrolled pregnant participants will be randomly assigned to either an intervention group or a pamphlets-only comparison group.

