Intervention Group: a one-on-one session with a project officer using motivational interviewing to examine current lifestyle choices (regarding alcohol consumption) and develop a tailored change plan to identify steps the participant can take to change a current lifestyle choice. Once a participant enrolls into the Motivational Enhancement Therapy (MET) study and is randomized to the Intervention Group, each will be provided a brief MET session, provided a call in number, and monitored up to five times throughout the pregnancy.

Comparison Group (pamphlets only): receive pamphlets on the dangers of alcohol consumption during pregnancy.

Both Groups: Women in both groups will be interviewed at enrollment and 9 months follow-up. All mothers enrolled in the Intervention Group and Comparison Group will be asked to provide blood spot samples at 3 time points: 1) on the same day the antenatal screening questionnaire is completed, 2) once during the third trimester of the pregnancy (between 30- and 34 weeks gestation), and 3) within 30 days after the birth of the baby. Obtaining the blood spot samples will take about 10-15 minutes and will be performed by an experienced research staff member. Blood spots will be collected by pricking the finger with a sterile safety lancet. The collector will wear latex free gloves and use universal precautions (five small drops of blood will be collected). Blood spots will be collected on de-identified, sterile blood spot collection cards and will be shipped to United States Drug Testing Laboratories, Inc (USDTL) for processing for detection of phosphatidylethanol (PEth) levels. Infants of both groups will be assessed with standard neurodevelopmental assessments (Bayley Scales of Infant Development)²⁰ and standardized physical assessment for growth, development, and dysmorphology.^{21,22}

Randomization

Random assignment numbers will be picked via a computerized random number selection program to indicate who is assigned to the Intervention Group and who is assigned to the Comparison Group. The randomization ratio will be 1:1. There is no blinding or masking.

DATA COLLECTION AND MANAGEMENT

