The PI will be responsible for monitoring participant data for safety concerns, adverse events, and serious adverse events. Any unanticipated problems will be reported promptly in compliance with Good Clinical Practice. Staff will notify participants of new safety information as soon as possible. Women requiring additional medical attention will be given the contact information for local providers and guided to referrals by staff.

There is no prospect of benefit for the woman or the fetus involved in this research, the risk to the fetus is not greater than minimal, and the purpose of the research is the development of important biomedical knowledge which cannot be obtained by any other means. The risks to the participants of this project will be minimal. The research focuses on the general health and behavioral factors that participants may possess which put a fetus at risk. When maternal interviews are carried out, a unique consent form is signed by the female interviewee. All information from the interview is confidential. Participants are protected by using standard conservative protocols and the protection of privileged information. Screening, confidential record reviews, and some of the research activities have strict record protection protocols. Communication styles will be monitored by the research team. Consent forms are signed emphasizing the voluntary nature of the services, that they are oriented to research, and that participants can disengage from the study at any time with no penalty.

WITHDRAWL

Participants may withdraw from the study at any point. Participants who voluntarily withdraw may keep previously given incentive amount.

STATISTICAL ANALYSIS PLAN

Primary Endpoint: Change in Alcohol Use Disorder Identification Test (AUDIT) score.

Data Analysis Plan: The primary outcome is the change in AUDIT score from baseline to 9 months follow-up. Between-group mean differences and standard deviations will be compared. Data analysis will include traditional statistical analyses for group differences.

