Power Analysis: The primary test is that women in the Intervention Group should show greater reduction of alcohol consumption over time than women in the Comparison Group. Main effects of time are expected because alcohol consumption should be reduced as a result of first contact. Therefore, a group (between) effect, time (within) effect, and a group by time interaction will be explored. With a sample size of 400, alpha = .05, power of 0.95, there is power to detect an effect size (f) of .09. With a sample size of 200, there is power to detect an effect size of .13.

Data Integrity: Data will be subjected to standard quality control and assurance measures.

PLANS FOR PUBLICATION

Aggregate, anonymous data will be presented in standard scientific publications and conferences. The utilization of final publication information only in anonymous and aggregate form protects the identity of both individuals and communities. Groups and/or subgroups will not be small enough to allow individuals to be deductively identified.

REFERENCES

1. May, P. A. *et al.* Prevalence of Fetal Alcohol Spectrum Disorders in 4 US Communities. *J Am Med Assoc* **319**, 474–482 (2018).
2. May, P. A. *et al.* Approaching the Prevalence of the Full Spectrum of Fetal Alcohol Spectrum Disorders in a South African Population-Based Study. *Alcohol Clin Exp Res* **37**, 818–830 (2013).
3. May, P. A. *et al.* The Continuum of Fetal Alcohol Spectrum Disorders in a Community in South Africa: Prevalence and Characteristics in a Fifth Sample. *Drug Alcohol Depend* **168**, 274–286 (2016).
4. May, P. A. *et al.* The Prevalence, Child Characteristics, and Maternal Risk Factors for the Continuum of Fetal Alcohol Spectrum Disorders: A sixth Population-Based Study in the Same South African Community. *Drug Alcohol Depend* **218**, 108408 (2021).
5. May, P. A. *et al.* The Continuum of Fetal Alcohol Spectrum Disorders in Four Rural Communities in South Africa: Prevalence and Characteristics. *Drug Alcohol Depend* **159**, 207–218 (2016).
6. May, P. A. *et al.* Replication of High Fetal Alcohol Spectrum Disorders Prevalence Rates, Child Characteristics, and Maternal Risk Factors in a Second Sample of Rural Communities in South Africa. *Int J Environ Res Public Health* **14**, 522 (2017).

7. Croxford, J. & Viljoen, D. Alcohol consumption by pregnant women in the Western Cape. *South African Medical Journal* **89**, 962–965 (1999).

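### Are the detectable effect sizes of .09 and .13 wrong, given that the power paragraph leaves out the correlation, the effect tested and any allowance for loss?

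*Combined protocol and SAP*

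**What the plan says.** The Power Analysis paragraph first describes the primary test in words: "women in the Intervention Group should show greater reduction of alcohol consumption over time than women in the Comparison Group". It then says "Therefore, a group (between) effect, time (within) effect, and a group by time interaction will be explored". Two detectable effects follow: "With a sample size of 400, alpha = .05, power of 0.95, there is power to detect an effect size (f) of .09", and "With a sample size of 200, there is power to detect an effect size of .13". Alpha and power are not repeated for the second figure and are taken to carry over.

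The Data Analysis Plan fixes the outcome: "The primary outcome is the change in AUDIT score from baseline to 9 months follow-up". The Procedures section gives two measurement occasions: "Women in both groups will be interviewed at enrollment and 9 months follow-up". The Randomization section sets a 1:1 ratio. The Procedures section also sets the enrolment ceiling: "Up to 400 women will be enrolled into the intervention study". The section on withdrawal states "Participants may withdraw from the study at any point".

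No section gives a correlation between the two AUDIT scores, a one- or two-sided choice, or an expected loss rate.

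**The concern.** An f value in a repeated-measures design has no fixed meaning until the effect and the correlation are known. The sentence just before the figures lists three effects, and the figures are not attached to any one of them. The choice matters. At f = .09 with 400 women, the power is about .95 for the group-by-time test at a correlation of 0.5, about .55 for the group main effect at that correlation, and about .43 if f is taken as a one-way effect size on change scores. The last reading is tempting because the Data Analysis Plan describes a direct comparison of change.

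The second worry is the count. The sample size of 400 in the power statement equals the enrolment ceiling, women may withdraw, and the calculation needs an AUDIT at both interviews. If the figures belonged to the wrong test, or silently assumed full follow-up in a study that expected heavy loss, the trial could be much less sensitive than stated and a null result could be misread.

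**Working it through.** **Inputs from the documents.** Two groups, 1:1 (Randomization); m = 2 measurements (Procedures); alpha .05, power .95, N = 400 with f = .09 and N = 200 with f = .13 (Power Analysis).

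**Assumed, because not stated.** Correlation r between enrolment and 9-month AUDIT, 0.5 unless shown otherwise; two-sided testing (an F test at .05).

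**Step 1: reproduce the plan's figures.** For the group-by-time test, lambda = f² × N × m / (1 − r), with 1 and N − 2 degrees of freedom.

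- N = 400, f = .09: lambda = .0081 × 400 × 2 / 0.5 = 12.96; power .949.
- N = 200, f = .13: lambda = .0169 × 200 × 2 / 0.5 = 13.52; power .955.

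Solving for power of exactly .95 gives f = .0903 at 400 and .1281 at 200. These round to the stated .09 and .13.

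**Step 2: confirm that this is the primary comparison.** With two groups and two occasions, the between-group difference in mean change is 4f × sigma, and the SD of change is sigma × √(2(1 − r)). The standardised difference in change is therefore d = 4f / √(2(1 − r)). A two-sample comparison of change has lambda = N × d² / 4 = N × 16f² / (4 × 2(1 − r)) = 2N × f² / (1 − r), which is the lambda of Step 1. So the interaction test and the comparison of AUDIT change are one test.

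At power .95, d = 0.361 for 400 and 0.512 for 200. These do not depend on r.

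**Step 3: try the other readings (power .95, r = 0.5).**

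| Reading | Detectable f, N = 400 | Detectable f, N = 200 |
|---|---|---|
| Group by time | .090 | .128 |
| Time | .090 | .128 |
| Group main effect, lambda = f² × N × 2 / (1 + r) | .156 | .222 |
| One-way on change scores, lambda = f² × N | .181 | .256 |

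Of these readings, only the group-by-time and time effects give both stated values, and only the first is the primary test as described.

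**Step 4: range of r.** Both stated values round correctly for r of about .45 to .52 if the test is two-sided. If it is one-sided at .05 (treated as an F test at .10), the range is about .34 to .43. For assumed r, two-sided, power at the stated f is:

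| r | N = 400, f = .09 | N = 200, f = .13 |
|---|---|---|
| .3 | .859 | .871 |
| .4 | .906 | .916 |
| .5 | .949 | .955 |
| .6 | .980 | .983 |
| .7 | .996 | .997 |

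**Step 5: loss to follow-up.** The documents give no rate, so 10, 20 and 30% are assumptions, with r = 0.5.

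| Enrolled | Women with both AUDITs | Power at stated f | Detectable f | Detectable d |
|---|---|---|---|---|
| 400 | 360 | .926 | .095 | 0.38 |
| 400 | 320 | .894 | .101 | 0.40 |
| 400 | 280 | .851 | .108 | 0.43 |
| 200 | 180 | .934 | .135 | 0.54 |
| 200 | 160 | .905 | .143 | 0.57 |
| 200 | 140 | .863 | .153 | 0.61 |

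For 400 enrolled, each detectable f lies between the plan's own .09 and .13.

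**The case for a change.** The strongest case for a change is that one printed number can mean power of .95, .55 or .43 depending on a choice that is not written beside it, and that two or three sentences would settle it. The N = 200 figure is not presented as an attrition scenario, so strictly the plan says nothing about loss. Someone trying to reproduce f has to guess r, and a clearer paragraph would help a null result to be read on the right scale.

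Much of this is true. The f values are not explicitly tied to the interaction, and r, sidedness and expected loss are absent. The paragraph also words its test as alcohol consumption where the endpoint is AUDIT change.

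It does not amount to a fault that needs repair. The paragraph does name the group-by-time interaction and opens by describing the primary test in those terms, so the natural reading is also the one that reproduces the figures. The missing r does not block interpretation on the SD-of-change scale, where it cancels. Conversion to AUDIT points would also need an AUDIT SD, which the documents do not give and a stated r would not supply. Writing r = 0.5 into the plan would record a value solved back from the answer as if the planners had chosen it, and if the test were one-sided that value would not fit. On loss, a right to withdraw implies no rate, and the power statement is conditional on its N.

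**Conclusion.** The concern does not call for a change. The stated .09 and .13 are consistent with the group-by-time test of AUDIT change at two interviews, with a correlation near 0.5 under two-sided testing, or about .34 to .43 if one-sided. On the two-sided reading the trial can detect differences of about 0.36 SD of change with 400 women and 0.51 SD with 200, when N counts women who have both AUDITs.

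If 30% of 400 enrolled women lacked the 9-month score, power at f = .09 would be about .85 and the detectable difference about 0.43 SD. That rate is an assumption, and nothing in the documents indicates that it or any other rate applies.

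What is missing is supporting detail for a calculation that reproduces. A statistician can recover the test from the paragraph and its SD-of-change equivalent by arithmetic. The sponsor could confirm the effect, correlation, sidedness and basis of N on request, but the answer would leave the design, the enrolment ceiling, the analysis and the conclusions as they are.
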